The intubation modalities (GlideScope, Macintosh laryngoscope, GlideRite stylet and DLT intubating stylet) have all been approved for clinical use and have been used routinely at our institution for DLT placement.

Macintosh blade is one of the most commonly used direct laryngoscopy blades for both single and double-lumen endotracheal intubations. It allows the practitioner to visualize larynx for subsequent intubation.

The **GlideScope** is a video laryngoscope that provides a real-time view of the airway and tube-placement during intubation in place of the direct laryngoscope.

The **GlideRite Rigid stylet** is specifically designed to work with the GlideScope video laryngoscope to facilitate intubation. It provides necessary rigidity and curvature to an otherwise flexible endotracheal tube to permit easier manipulation of it for tracheal intubation.

ZU-bend is a specific shaping technique of the intubating stylet that is more closely related to GlideScope blade curvature. There is a commonplace practice of shaping a flexible stylet for intubation to suit a particular combination of patient and equipment variables. The degree of shaping is somewhat specific to each provider, and is a normal procedure for using the intubating stylet. Bending of the stylet prior to intubation constitutes a routine preparation step for the majority of intubations. The steps for shaping of the stylet are provided in the appendix A.

Objectives

The current research does not provide clear support for one method or another in DLT placement techniques. Additionally, our research has shown that the ZU-bend stylet may be useful with the GlideScope. This randomized controlled study will compare the efficacy of three different methods of DLT placement.

The primary outcome measures will be the mean time it takes to place a DLT with each modality. Secondary outcome measures include success rate of first endobronchial intubation attempt; assessment of difficulty by the provider and complication incidence.

The end points of evaluation of each technique were selected based on Russel's protocol with our modification as summarized in Table 1:

Table 1.

Metric:	Defined as:
First intubation attempt success	DLT placed during initial laryngoscopy, within 120s
Duration of laryngoscopy	Time from laryngoscope at pt's lips through 1 st EtCO ₂ detection
Blood on device	Yes/No
SpO ₂ <96% during intubation	Yes/no
Voice changes	Evaluated in PACU - subjective answer by patient

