Lip trauma	Evaluated immediately post-intubation
Dental trauma	--/--
Sore throat	Analog pain scale 0-10, subjective answer in PACU
DLT cuff rupture	Loss of air pressure during procedure requiring >1 reinflation
Ease of device placement	Multi-question form to be filled by anesthetist after intubation
Overall ease of intubation	Subjective score 0-10; where 0 – worst, 10-best
Laryngoscope insertion	--/--
Glottic view	--/--
DLT delivery	--/-- placement of DLT mouth → into glottis proximity
DLT placement	--/-- ease of placing DLT through glottic opening

Study design and methods

This is a prospective, randomized, three-armed trial to investigate the efficacy of a radically curved DLT stylet to facilitate GlideScope-assisted tracheal intubation (Group 1) as compared to the commercial standard of GlideScope with GlideRite stylet (Group 2) and a direct laryngoscopy with Macintosh blade and a regular DLT stylet (Group 3).

This study will not impart additional risks on the patient in excess of those routinely cited for placement of the double-lumen endobronchial tube. All of the modern intubation modalities will be available at the intubation time, arguably decreasing the risk of an ultimately failed securing of patient's airway.

Following informed consent, each subject will be identified via a unique alpha-numeric code and randomized to either of 3 initial DLT placement technique groups. In all cases, the other 2 intervention modalities will be available in the event of failed 1st attempt intubation and will be used at practitioner's discretion. Patient's medical history and detailed airway exam will be recorded on the study form, including Mallampatti score, thyromental distance, ability to prognathize the mandible, any limitation in neck flexion/extension, any evidence of poor dentition or pre-existing dental damage, patient's height, weight and BMI.

Patient will then be taken to the operating room and anesthesia will be induced in the standard fashion per provider's discretion after denitrogenation of patient with 100% O₂ until EtO₂ value is greater or equal to 80%.

Laryngoscopy with the specified randomization modality will be performed by the anesthetist or fellow with timing of intubation recorded as described above. DLT size used will be recorded on the form as well.

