The placement of DLT will be verified in a standard fashion using fiberoptic bronchoscopy, auscultation and capnometry. The anesthetist/fellow then will complete their experience questionnaire portion of evaluation. After the conclusion of the procedure, patient will be extubated using standard ASA guidelines and taken to the Post-Operative Admission Unit (PACU), where the final evaluation of patient will take place, assessing voice change and throat pain as described above. This will conclude our study period and patient care will be resumed.

Human Selection Criteria

We plan to enroll up to 130 subjects in order to achieve 120 evaluable subjects with 40 in each arm at Emory University Hospital (EUH) and Emory University Hospital Midtown (EUHM). We will include patients that are scheduled for a thoracic surgical intervention in which surgeon requests lung isolation, including but not limited to: VATS, open thoracic surgery for lung or esophageal disorder, thoracic duct intervention, sympathectomy procedure.

Inclusion Criteria

- Male and female patients requiring DLT placement for their surgery at EUH or EUHM
- Patients willing and able to provide written informed consent

Exclusion Criteria

- Patients in whom a previously difficult airway manipulation was recorded on an anesthetic record.
- Lung transplantation procedures, as underlying pulmonary disorder will confound SpO₂ metric.
- Any patient who is receiving anticoagulants in excess of a daily aspirin, patients with INR >1.4
- Patients in whom one lung ventilation or placement of DLT is contraindicated.
- Patients who require a rapid-sequence intubation.
- Patients undergoing emergency procedures.

Patients who meet eligibility based upon the above criteria will initially be screened by the study team in concert with the patient care team. The study design will be explained to the patient and their interest assessed. Sufficient time will be allotted for the patient to discuss the study in detail with a study investigator, read the informed consent, ask any questions, and sign the informed consent prior to performing the study protocol. This will permit final confirmation that the patients who are enrolled in the study do not have airway anatomy consistent with an expected difficult airway and therefore meeting exclusion criteria for this study.

Estimated time to completion of study: 24 months from enrollment of first subject.

Statistical Analysis

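### Voice change and sore throat are asked once in PACU at no set time, with no required pre-operative question and no statement on concealing the arm: knowledge of the arm could bias the answers, and the other gaps mainly dilute true differences

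*Combined protocol and SAP*

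**What the plan says.** Table 1, under Objectives, defines voice changes as "Evaluated in PACU - subjective answer by patient", with no scale, threshold, question wording or time. It defines sore throat as "Analog pain scale 0-10, subjective answer in PACU", which supplies a scale but no time.

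Study design and methods sends the patient after extubation to PACU, "where the final evaluation of patient will take place, assessing voice change and throat pain as described above". The next sentence reads "This will conclude our study period and patient care will be resumed", so there is no later assessment. The person who asks the questions is not named.

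Before surgery, the same section states: "Patient's medical history and detailed airway exam will be recorded on the study form, including Mallampatti score, thyromental distance". The list goes on through jaw and neck mobility and body size, and includes "any evidence of poor dentition or pre-existing dental damage". It contains no voice or throat item.

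The design statement is "This is a prospective, randomized, three-armed trial to investigate the efficacy of a radically curved DLT stylet". Neither it nor any other part of the document mentions masking. On the order of events, the plan says "Patient will then be taken to the operating room and anesthesia will be induced in the standard fashion per provider's discretion", with laryngoscopy in the assigned arm following.

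Complication incidence is a secondary outcome under Objectives; the primary is mean placement time. Human Selection Criteria gives 40 evaluable subjects per arm. Statistical Analysis names Fisher's exact test for categorical data, and Mann-Whitney or t-tests for continuous data.

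**The concern.** Comparing complications between techniques is one of the trial's stated aims, and these two items are the only ones in Table 1 that come from the patient. Three features weaken them, in different ways.

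- **Arm not stated to be concealed.** A patient or interviewer who knows the technique can shift a subjective answer. The Introduction and Objectives report the team's own favourable experience with the ZU-bend, so expectation is a realistic influence. This route can create a difference that is not there, or hide one that is.
- **No required baseline.** Voice change is by name a change measure, and the trial enrols patients with lung and oesophageal disease. Hoarseness present before surgery may be counted as if the technique had caused it. The plan sees the need elsewhere: it records existing dental damage, which gives dental trauma a baseline.
- **No set time.** Any moment in PACU qualifies, from a patient barely awake to one ready to leave.

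Under randomisation the last two act similarly in every arm, so they mainly hide true differences. For a harm, that means false reassurance: a technique that causes more voice change could appear no worse than the others.

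**Working it through.** **What the plan allows to be reproduced.** The plan gives no figure for either outcome. Its 40 per arm is stated without alpha, power, effect size, SD or event rate, so power for these outcomes cannot be reproduced. The enrolment figures are consistent: 130 enrolled for 120 evaluable allows a loss of 10/130 = 7.7%.

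**Inputs.** From the documents: 40 per arm and Fisher's exact test. Assumed: two-sided 5% level, pairwise comparisons, and every rate, SD and shift below.

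**1. Voice change: dilution by existing hoarseness.** Assume technique-caused rates of 10% and 30%, and let *b* be the share of patients already hoarse.

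- Worst case without a baseline: every already hoarse patient answers that the voice has changed. Observed rate = *b* + (1 − *b*) × *p*. At *b* = 0.2 this is 0.2 + 0.8 × 0.10 = 28% and 0.2 + 0.8 × 0.30 = 44%.
- New-or-worse scoring, taking the pessimistic view that an already hoarse patient cannot register as worse: observed rate = (1 − *b*) × *p*. At *b* = 0.2 this is 8% and 24%.

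Power is the exact sum, over all pairs of counts with Fisher *p* ≤ 0.05, of the two binomial probabilities:

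| Background *b* | No baseline, worst case: rates | Power | New-or-worse: rates | Power |
|---|---|---|---|---|
| 0% | 10% v 30% | 53% | 10% v 30% | 53% |
| 10% | 19% v 37% | 35% | 9% v 27% | 47% |
| 20% | 28% v 44% | 24% | 8% v 24% | 40% |
| 30% | 37% v 51% | 19% | 7% v 21% | 33% |

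On these assumptions the baseline question recovers (47 − 35)/(53 − 35) = 12/18, (40 − 24)/(53 − 24) = 16/29 and (33 − 19)/(53 − 19) = 14/34 of the lost power. That is about two-thirds, just over half and about two-fifths.

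**2. Sore throat: a reporting shift that depends on the arm.** Assume SD 2.5 and no true difference. SE = 2.5 × √(2/40) = 0.56. By normal approximation, the chance of a significant result is Φ(−1.96 − shift/SE) + 1 − Φ(1.96 − shift/SE).

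- No shift: 5%.
- Shift 0.5: 0.5/0.559 = 0.894, giving 14.5%.
- Shift 1.0: 1.0/0.559 = 1.789, giving 43.2%.

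**3. Sore throat: noise from variable timing.** Assume a true difference of 1.5 points and SD 2.5. Power by the two-means formula is 77% with no added noise. With added noise of SD 1 the total SD is √(2.5² + 1²) = 2.69 and power is 70%; with added noise of SD 2 it is √(2.5² + 2²) = 3.20 and power is 55%. This loss arises with no bias at all.

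**The case against.** **Masking is argued from silence.** A reader might infer that the trial is unmasked and that staff who saw the intubation will ask the questions. The documents do not say so. Randomisation after consent does not mean that the patient is told the arm. The consent pages are not available and the study form is not reproduced, so what patients are told, the question wording and any time field cannot be checked. What stands is that the plan leaves this unspecified and so permits an interviewer who knows the arm.

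**The question already asks for a comparison.** Asking about a change invites the patient to compare with before, and stable hoarseness is not a change. Medical history is recorded and the baseline list is not exhaustive, so hoarseness may be noted. This is fair, and it makes the no-baseline column in the table a worst case. But nothing requires the item, and the comparison then rests on unscripted recall soon after anaesthesia.

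**Timing and background are noise.** A reader might take all three gaps as sources of bias. Under randomisation, unfixed timing and background symptoms do not bias the comparison unless they differ by arm, and nothing in the plan suggests that they would. Dilution remains.

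**The figures are assumed.** They are. A 1-point mean shift across a whole arm is large. Even with perfect measurement, power for 10% v 30% is only about 53%, so sample size is itself a serious limit.

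**Conclusion.** The point holds in a limited form. Both patient-reported complications rest on one PACU answer at no set time, without a required baseline and without any statement on whether patient or interviewer is kept unaware of the arm. Concealment is feasible for both, though not for the person intubating. Knowledge of the arm is the real route to bias; the missing baseline and open timing mainly reduce the chance of seeing a true difference.

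The sizes are illustrations, because the documents give no hoarseness rate, sore-throat SD or reporting shift. At 10-30% background hoarseness, power falls from 53% to between 35% and 19% in the worst case, and a baseline question brings it back to between 47% and 33% under the pessimistic scoring assumption. It would be wrong to read the table as saying that a baseline restores the full 53%. Arm-dependent shifts of 0.5 and 1 point would raise sore-throat false positives from 5% to about 15% and 43%.

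These are two items within one secondary outcome, and the comparison of placement time is untouched. The changes are still worth making, because a baseline or concealed answer not collected at the time cannot be recovered at analysis.

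**What to change.** 1. State that the arm is not disclosed to the patient until the PACU questions have been answered. Have existing staff, or a team member not present at intubation, read the two questions from a fixed script and record the answers on a sheet that does not show the arm.
2. Ask the same two questions at the existing pre-operative airway exam. Score voice change as new or worse than baseline, and compare sore throat with allowance for its baseline score.
3. Set a target time window after PACU arrival and record the actual time of the answers.

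The cost is two extra questions, a separate PACU sheet and a few protocol sentences. Some answers will fall outside the window. The documents do not describe PACU staffing, so the sponsor should confirm at both hospitals that someone who was not at the intubation is available to ask. Sample size, techniques and clinical care do not change.

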The protocol in Russel's paper and previously cited data within their paper indicated that statistical significance can be attained at 30 subjects in each arm for 2 intervention comparison.

In our evaluation with 3 treatment arms, increasing sample size to 40 patients should provide adequate statistical power. Categorical data will be analyzed using Fisher's exact test. Mann-Whitney and Student's t-test will be applied where appropriate for continuous variables.

Adverse Event Reporting

The study team will comply with Emory University IRB policies for reporting adverse events. In this study, events that are determined by the Principal Investigator to be related to the research will be recorded and reported. Additionally, all deaths, related or unrelated, will be reported to the IRB. All events that are unanticipated problems that are related or possibly related to the research and place the subject or others at greater risk of harm than anticipated will be immediately reported to the Emory IRB.

Data and Safety Monitoring Plan

The data will be continuously analyzed to ensure there is not a significant trend that warrants early termination of the study. The PI will conduct monitoring after the first 10 patients are enrolled and again halfway through the study at 60 patients to evaluate for any related adverse events and ensure continued patient safety. Any serious complications encountered by the anesthesiologist in the room will be relayed to the principal investigator or co-investigators.

All investigators will complete the required training for conducting research at Emory University. All investigators will be made aware of the adverse event reporting policy and will report these events to the principal investigator in a timely manner.

References

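### Lip and dental trauma are checked once, with the tube in place, and not in PACU, so injuries noticed after extubation can be missed by the complication endpoint

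*Combined protocol and SAP*

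**What the plan says.** Complications are a stated aim. The Introduction proposes to compare complication rates between techniques, and the Objectives list among the secondary outcomes "assessment of difficulty by the provider and complication incidence".

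Table 1 defines each metric. Lip trauma is "Evaluated immediately post-intubation". The next row, "Dental trauma", has only a ditto mark, which I read as the same timing. Voice changes and sore throat, by contrast, are answered by the patient in PACU.

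Under Study design and methods, the preoperative record includes "any evidence of poor dentition or pre-existing dental damage". After surgery and extubation the patient goes to PACU, "where the final evaluation of patient will take place, assessing voice change and throat pain as described above". The next sentence closes follow-up: "This will conclude our study period and patient care will be resumed".

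The Adverse Event Reporting section adds a general route: "events that are determined by the Principal Investigator to be related to the research will be recorded and reported".

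**The concern.** The single look at lips and teeth comes just after a double-lumen tube has been placed, while the tube is still in the mouth and its position has to be verified by bronchoscopy, auscultation and capnometry. The patient is anaesthetised and cannot report a loose tooth or a sore lip. By the PACU visit the tube is out and the patient can answer questions, but lips and teeth are not on the list.

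The protocol already collects the dental baseline that would let a later check tell new damage from old, but it plans no later check to set against it.

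At stake is how complete the complication count is. If some injuries come to light only after extubation, trauma incidence will be too low in every arm and differences between techniques will look smaller than they are. A low observed rate would then be weaker reassurance about harm than it appears.

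**Working it through.** The point rests on when assessments are made, and the plan states no figure to reproduce for it. I set the places side by side first, then show what under-detection does under stated assumptions.

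**Where a lip or dental injury can be recorded**

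| Time | What the protocol plans | Lips and teeth covered? |
|---|---|---|
| Before induction | Airway exam, including dentition and existing dental damage | Teeth yes; lips not listed |
| Immediately after intubation | Table 1 trauma rows | Yes, both |
| PACU | Voice change, throat pain | No |
| After PACU | Study period over | No |
| Any time | Adverse events that the principal investigator judges research-related | Only if so judged; not linked to Table 1 |

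An injury first noticed after extubation falls in the third row or later. No planned check looks for it.

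**Effect on the comparison**

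Inputs from the documents: 40 evaluable patients per arm (Human Selection Criteria) and Fisher's exact test for categorical data (Statistical Analysis). Assumptions, because the documents are silent: two-sided 0.05, the true trauma rates p1 and p2, and a share s of injuries found at the immediate check, equal in all arms, with no false positives.

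Observed risk difference = s × p2 − s × p1 = s × (p2 − p1).

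Example with p1 = 5% and p2 = 15%:
- Full detection: 2/40 v 6/40, a difference of 10 points, Fisher p = 0.26.
- Half detected: 1/40 v 3/40, a difference of 5 points, Fisher p = 0.62.

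The difference is halved, but neither result would be significant.

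Power of the Fisher test at 40 v 40, by full enumeration of both binomial distributions:

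| Assumed true rates | s = 1 | s = 0.9 | s = 0.75 | s = 0.5 |
|---|---|---|---|---|
| 5% v 15% | 18% | 15% | 10% | 3% |
| 5% v 25% | 65% | 57% | 44% | 19% |
| 10% v 30% | 53% | 47% | 37% | 18% |

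Two things follow. Power for these comparisons is limited even when every injury is found. Missed injuries lower it further, by an amount that depends wholly on s, about which the documents say nothing.

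**The case against.** The strongest reply is that the timing suits the question. The trial compares placement techniques, and bronchoscopy, the operation and extubation all come between intubation and PACU. A check straight after intubation ties injury to laryngoscopy and tube placement. An observer can inspect lips and teeth in an anaesthetised patient, whereas voice and throat symptoms need the patient's answer. This stands as a reason to keep the immediate check. It is not a reason to have no later one, provided the two results are reported separately.

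A second reply is that adverse-event reporting provides a later route. That is partly right: the section sets no time limit tied to intubation, and the principal investigator reviews related adverse events after 10 and 60 patients. But the route depends on a judgement of relatedness to the research, it does not ask every patient the same question, and it does not feed Table 1. The protocol also says the study adds no risk beyond routine tube placement, so a chipped tooth could reasonably be judged unrelated to the research.

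Two stronger readings are tempting, and the documents support neither.

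- A reader might infer that an injury found on waking is scored as no complication. Table 1 gives these two rows a timing only and no coding rule for later findings. What can be said is that such an injury may be absent from the endpoint.
- A reader might infer that under-counting differs by arm because those in the room know the technique. The documents do not name the assessor or describe blinding for these items, but the same check applies in every arm and nothing shows unequal detection. Assessor knowledge is a separate matter, which a PACU check alone would not settle.

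**Conclusion.** The concern holds in a limited form. Followed as written, the protocol has no systematic way to count lip or dental injury that becomes apparent after extubation, although complication incidence by technique is a secondary outcome. The expected consequence is under-counting in all arms and observed differences shrunk towards zero.

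That direction rests on equal detection across arms and on the ditto mark meaning the same timing for dental as for lip trauma. The size cannot be estimated: the rates and detection shares used above are illustrations. In the 5% v 15% example no conclusion changes, and at 40 per arm a low trauma rate would be weak evidence of similar safety whatever the timing. The protocol plans no equivalence claim on these items.

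The reach is small: two items within one secondary outcome, with no effect on placement time. This is a cheap improvement, not a flaw that threatens the trial.

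**What to change.** 1. Keep the immediate check as it is, and name it as the technique-attributable result.
2. Add to the existing PACU evaluation a brief lip and dental inspection and one patient question about any new tooth or lip injury, compared with the preoperative dental record.
3. Add lip condition to that preoperative record, so that new lip injury can also be told from old.
4. Report three results for each item by randomised arm: immediate, PACU, and either.

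The cost is about two lines on the PACU form and one on the baseline form, at contacts that already take place. The downside is that the PACU check may also pick up injury from extubation or later airway instrumentation. That is why the immediate and PACU results should be kept separate and not merged into one figure.

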Title:

Comparison of placement of double-lumen endobronchial tube using Glide Scope with 2 different stylet configurations vs standard Macintosh laryngoscopy.

Principal Investigator:[name], Emory University School of Medicine

V. 03April2015

NCT02495259

Title: Comparison of placement of double-lumen endobronchial tube using GlideScope with 2 different stylet configurations vs standard Macintosh laryngoscopy.

Principal Investigator: [name]
Emory University School of Medicine
Department of Anesthesiology

Site: Emory University Hospital (EUH) and Emory University Hospital – Midtown (EUHM)

IRB: Emory University School of Medicine

Purpose of Study

To evaluate the technique of placement of the double-lumen endobronchial tube (DLT) using an included stylet that has been radically bent (ZU-bend) as compared to a commercial GlideRite stylet with the GlideScope and direct laryngoscopy using Macintosh laryngoscope.

Introduction

Placement of the DLT is viewed as more challenging partly due to bulkiness and a lack of flexibility that the DLT has compared to single lumen endotracheal tubes, as well as a larger and more fragile occlusion balloon that is more prone to rupture. Securing an airway using traditional laryngoscopy as well as video-assisted indirect laryngoscopy each has its unique advantages and disadvantages.

In a recent study comparing laryngoscopy with Macintosh blade and GlideScope the former was concluded to be superior with respect to intubation success (1), while an earlier study indicated GlideScope to be equivalent to direct laryngoscopy (4). A follow-up editorial pointed out that in Russel's study there was no inclusion of the GlideRite stylet designed specifically for use with GlideScope and DLT, possibly explaining difficulties with GlideScope-assisted intubations (2, 3).

In a small anecdotal sample, the use of a radically curved DLT stylet, the ZU-bend, and GlideScope appeared to be useful in placement of the DLTs by multiple anesthetists under supervision of one anesthesiologist ([name], presented at Thoracic Anesthesia Symposium 2015).

Therefore, we propose to merge the study protocol similar to Russel et. al. (1) with inclusion of both the suggestions from Bussier's editorial , as well as the experience with radically bent DLT stylet (ZU-bend) to evaluate each method with respect to intubation ease and to compare the complication rate with each technique.

Investigational Devices

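### The cuff rupture definition counts reinflations only, so read literally it can score an outright cuff failure that ends in tube exchange as no rupture

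*Combined protocol and SAP*

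**What the plan says.** Table 1 gives the only definition of DLT cuff rupture in the document: "Loss of air pressure during procedure requiring >1 reinflation". It has two parts, both needed: pressure is lost, and more than one reinflation is required.

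The item serves a stated aim. The Introduction lists "a larger and more fragile occlusion balloon that is more prone to rupture" among the features that make DLT placement harder, and says the trial will evaluate each method and "to compare the complication rate with each technique". The Objectives name "assessment of difficulty by the provider and complication incidence" among the secondary outcomes.

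For analysis, the Statistical Analysis section says "Categorical data will be analyzed using Fisher's exact test", and Human Selection Criteria plans for 40 evaluable subjects in each of three arms.

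**The concern.** The threshold counts attempts to go on using a cuff; it does not ask whether the cuff failed. A cuff that plainly cannot hold air is the one least likely to be reinflated twice. The worst form of the event can therefore fall outside the definition while a slower, recurrent leak falls inside it.

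The three arms differ in stylet and laryngoscope, so cuff damage during insertion is a plausible way for them to differ. If outright failures drop out of the count, the comparison of cuff complications loses events it can ill afford at 40 per arm.

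**Working it through.** **1. The rule applied case by case** (Table 1, literal reading)

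| What happens to the cuff | Reinflations | Scored as rupture? |
|---|---|---|
| Loses pressure, topped up once, then holds | 1 | No |
| Loses pressure, topped up twice or more | 2 or more | Yes |
| Loses pressure, topped up once, then tube exchanged | 1 | No |
| Torn, will not hold air, tube exchanged at once | 0 | No |

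The first row shows the sensible purpose of the threshold: it screens out a single top-up. The last two rows are the gap.

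**2. Is the gap closed elsewhere?**

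- No other row of Table 1 records tube exchange, a visibly torn cuff or a cuff that cannot be reinflated.
- First-attempt success depends on placement at the initial laryngoscopy within 120 s. A tube placed in time with a torn cuff can still be a success.
- Adverse Event Reporting and the Data and Safety Monitoring Plan cover research-related events, deaths, unanticipated problems and serious complications. Neither feeds this endpoint.

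So an outright failure followed by exchange could appear in no outcome count.

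**3. Illustration of size**

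The plan has no figure to reproduce here: it states no rupture rate, exchange share, alpha or sidedness.

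- From the documents: n = 40 per arm; Fisher's exact test.
- Assumed: a comparison of two arms; two-sided alpha of 0.05; true rupture rates of 20% and 5%; the same share m of ruptures uncounted in both arms.

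Recorded rate = true rate × (1 − m). Power is the sum, over all pairs of counts (i, j) with Fisher p ≤ 0.05, of Bin(i; 40, p1) × Bin(j; 40, p2), where p1 and p2 are the recorded rates.

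| m | Recorded rates | Expected counts of 40 | Ratio | Power |
|---|---|---|---|---|
| 0% | 20% v 5% | 8 v 2 | 4 | 0.411 |
| 10% | 18% v 4.5% | 7.2 v 1.8 | 4 | 0.345 |
| 25% | 15% v 3.75% | 6 v 1.5 | 4 | 0.245 |
| 50% | 10% v 2.5% | 4 v 1 | 4 | 0.094 |
| 75% | 5% v 1.25% | 2 v 0.5 | 4 | 0.009 |

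With assumed counts of 6 v 0, Fisher p = 0.026. If one of the six goes uncounted, 5 v 0 gives p = 0.055; if two do, 4 v 0 gives p = 0.116. At counts this small, a single misclassified failure can move the result across 0.05.

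**4. What a reversal would take**

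Let m1 and m2 be the uncounted shares in the higher-rate and lower-rate arms. Recorded rates reverse only if 20% × (1 − m1) < 5% × (1 − m2), that is, (1 − m1)/(1 − m2) < 0.25. If the lower-rate arm misses none, the other arm must miss more than 75%.

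**The case against.** The strongest reply is that exclusion is not certain. The documents never mention tube exchange, and they show no scoring guide for this item. The row is headed as cuff rupture, and *requiring* can be read as need: a cuff that will not hold air needs more than one reinflation whether or not anyone performs it. An assessor facing a torn cuff might well mark Yes. This stands as a limit on how firmly undercounting can be asserted. It does not remove the defect, because two assessors could then score the same event differently, and the protocol describes no masked assessor for the item.

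A reader might also infer that the rule biases the comparison or could reverse it. The documents do not support that. Equal under-recording leaves the ratio at 4 in every line of the illustration, and nothing in the plan suggests that the share of ruptures ending in exchange differs between arms.

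Nor does the rule keep the mildest form of the event, since a leak cured by one top-up is excluded. And the Introduction offers cuff fragility as one factor beside bulk and inflexibility, not as the main one.

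Finally, power is only 41% under the assumed fourfold difference even with every rupture counted. Much of the weakness of this comparison comes from few events and 40 per arm. That is correct, and it limits how much the fix can recover.

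**Conclusion.** The point holds as a defect in an endpoint definition. Taken literally, the rule scores as No a cuff failure that leads to exchange after zero or one reinflation, and no other part of the plan catches it; taken loosely, scoring depends on the assessor. Either way, the most severe cuff failures can be undercounted.

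The reach is limited to one component of a secondary outcome. Placement time, which is the primary outcome, and the stated 40 per arm are untouched. The size cannot be fixed from the documents. The loss of power from 41% to 24%, 9% or 1% rests wholly on the assumed 20% v 5% rates and on assumed uncounted shares of 25%, 50% and 75%, equal in both arms. If only 10% went uncounted, power would be about 35%, a modest loss. The change is worth making because it is nearly free, not because a large effect has been shown.

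**What to change.** Reword the Table 1 entry along these lines: *loss of cuff pressure during the procedure that required more than one reinflation, or that led to exchange of the tube*. On the study form, record which of the two criteria was met, so that the existing definition can still be reported on its own.

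The cost is one line of Table 1 and one form field, with no added procedure and no added patients. The change concerns only how an event is scored. It says nothing about when a tube should be reinflated or exchanged.
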